3.2.2 Patient Population and Eligibility

Patients will be identified through selection of a diverse set of medical practices across the five targeted countries. To be eligible for the study, the patients must meet all of the following criteria:

- Patient has taken rivaroxaban within the last 3 months for prevention of stroke and systemic embolism in adult patients with non-valvular atrial fibrillation (SPAF) or

treatment of DVT and prevention of recurrent DVT and pulmonary embolism (PE) following an acute DVT in adults.

- Patient is aged 18 years or older.
- Patient is able to understand and complete the consent form and patient questionnaire.
- Patient can read and understand the native language of the country in which the study is being conducted.
- Patient has not participated in a clinical trial for a treatment to prevent blood clots in the past 12 months.

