3.2.3 Patient Selection and Recruitment

The study will target 100 patients per country to complete the assessment. This estimate is based upon the anticipated number of eligible patients for participation. This target study size is dependent upon the actual number of patients filling a prescription within the established time frame and on response rates for the study. At least 10 physician practices in each country will be selected from a list of eligible physicians in order to identify and recruit a sufficient number of eligible patients (up to 10 patients per physician). Several factors will be evaluated to ensure a diverse representation of sites, including geographic location, physician specialty, and patient mix. To participate in the study, sites must (1) see a sufficient number of eligible patients; (2) be able to provide a semiprivate space for patient recruitment, the consent process, and completion of the patient-reported questionnaire; and (3) have a staff member available to coordinate research activities.

Physicians who are selected to participate in the patient assessment will be excluded from participating in the physician assessment.

Participating physicians will also be asked to collect a limited amount of de-identified information on all patients receiving rivaroxaban so that characteristics of participants can be compared with non-participants.

Patients will be eligible if they have taken rivaroxaban within the last 3 months for either SPAF or DVT treatment and secondary prevention. The patient sampling methodology will be designed with the goal of maximising the probability that each patient treated with rivaroxaban will have an equal opportunity to be selected. In some sites, it is likely that all treated patients will be selected. The sampling approach for those sites with larger numbers of patients will be customised for the site (based on patient volume) and will be devised to achieve an efficient method of obtaining a representative patient sample in centres with varying patient administration systems. The sites will be asked to recruit the patients for the

study when the patient is at the physician practice for a previously scheduled visit, or by telephone.

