5 STRENGTHS AND LIMITATIONS

A key strength of the study is the diversity of the sites, physicians, and patient populations to be included in both assessments. Based on available information, geographic location, and physician practice type (clinic, hospital, internists, haematologists, etc.), sites and patients recruited for participation will constitute a generally representative sample of rivaroxaban prescribers and users. However, given the potential delay in product uptake, it might be challenging to ensure that the finally selected centres, prescribers, and patients are fully representative of the existing patient population across countries and different types of centres. Critical to the goal of capturing detailed patient information will be identification of physicians and patients who have been introduced to rivaroxaban and the newly approved indications.

The physician assessment will be conducted after physicians have received the prescriber guide and have had a chance to utilise that guide in their practice. This portion of the study will evaluate how physicians are using the materials in their daily practice with patients.

The patient questionnaire will be conducted after patients have received rivaroxaban. Therefore, the study will evaluate recall about the process of receiving and reading the patient alert card, awareness of the key information contained in the patient alert card, and whether the patient carries the patient alert card during treatment.

Among the strengths of the patient assessment will be the collection of information on participants and on non-participants. Sites will keep a simple log with information on the number of patients approached about the study, the number of patients confirmed eligible, and the number of patients who refused. Site logs will be produced weekly during the data collection period. These data will allow calculation of the participation rate. Patients who are approached by the study coordinator and then refuse to participate will be asked the reason for refusal. Reasons for non-participation will be described in the report. In addition, we will compare characteristics of the participants with those of the total rivaroxaban patients to evaluate any differences that should be considered in the analysis.

Other strengths of the patient assessment include the probability of high response rates given that the study is being introduced to patients by a trusted HCP, and the ability to

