However, during the continuous treatment phase, a reduction of the dose from 20mg once daily to 15mg once daily should be considered if the patient's assessed risk for bleeding outweighs the risk for recurrent DVT and PE. The recommendation for the use of 15mg is based on PK modelling and has not been studied in this clinical setting.

The use of Xarelto is not recommended in patients with creatinine clearance < 15 ml/min.

Duration of therapy:

The duration of therapy should be individualised after assessment of the treatment benefit against the risk for bleeding. Clinical surveillance in line with anticoagulation practice is recommended throughout the treatment period.

[figure not shown]
Missed dose:

- **Twice daily treatment period** (15mg bid for the first three weeks): If a dose is missed, the patient should take Xarelto immediately to ensure intake of 30mg Xarelto per day. Continue with the regular 15mg twice daily intake on the following day.
- **Once daily treatment period** (beyond three weeks): If a dose is missed, the patient should take Xarelto immediately and continue on the following day with the once daily intake as recommended. The dose should not be doubled within the same day to make up for a missed dose.

CONVERTING FROM VITAMIN K ANTAGONISTS (VKA) TO XARELTO

For patients treated for **prevention of stroke and systemic embolism**, treatment with VKA should be stopped and Xarelto therapy should be initiated when the international normalised ratio (INR) is ≤ 3.0 .

For patients treated for **DVT, PE and prevention of recurrent DVT and PE**, treatment with VKA should be stopped and Xarelto therapy should be initiated when the INR is ≤ 2.5 .

*See dosing recommendations for required daily dose

INR measurement is not appropriate to measure the anticoagulant activity of Xarelto, and therefore should not be used for this purpose. Treatment with Xarelto only does not require routine coagulation monitoring.

[figure not shown]

CONVERTING FROM XARELTO TO VKA

It is important to ensure adequate anticoagulation while minimising the risk of bleeding during conversion of therapy.

When converting to VKA, Xarelto and VKA should overlap until the INR is ≥ 2.0 . For the first two days of the conversion period, standard initial dosing of VKA should be used followed by VKA dosing guided by INR testing.

*See dosing recommendations for required daily dose

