Appendix B.
Xarelto Patient Alert Card

What should I know about Xarelto®?

- Xarelto® thins the blood, which prevents you from dangerous blood clots.
- Xarelto® must be taken exactly as prescribed by your doctor. To ensure optimal protection from blood clots, **never skip a dose.**
- You must not stop taking Xarelto® without first talking to your doctor as your risk of blood clots may increase.
- Speak to your health care provider prior to any intake of other medication.
- Inform your health care providers about Xarelto® intake prior to any surgery or invasive procedure.

When should I seek advice from my health care provider?

When taking a blood thinner such as Xarelto® it is important to be aware of its possible side effects. Bleeding is the most common side effect. Do not start taking Xarelto® if you are at risk of abnormal bleeding, without first discussing this with your doctor.

Tell your health care provider right away if you have any signs or symptoms of bleeding such as the following:

- pain
- swelling or discomfort
- headache, dizziness or weakness
- unusual bruising, nosebleeds, bleeding of gums, bleeding from cuts that take a long time to stop

- menstrual flow or vaginal bleeding that is heavier than normal
- pink or brown urine, red or black stools
- coughing up blood, or vomiting blood or material that looks like coffee grounds.

How do I take Xarelto®?

- To ensure optimal protection, Xarelto® 15mg and 20mg must be taken with food.

Date of preparation: November 2012
L.GB.10.2012.0954

PATIENT ALERT CARD

Xarelto® 15mg
Xarelto® 20mg

- **Keep this card with you at all times**
- **Present this card to every physician or dentist prior to treatment**

I am under anticoagulation treatment with Xarelto® (rivaroxaban)

Name: _____

Address: _____

Birth date: _____

Blood type: _____

Weight: _____

Other medications/conditions: _____

In case of emergency, please notify:

Doctor's name: _____

Doctor's phone: _____

Doctor's stamp: _____

Please also notify:

Name: _____

Phone: _____

Relationship: _____

Information for health care providers:

- INR values should not be used as they are not a dependable measure of the anticoagulant activity of Xarelto®.

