Appendix D.

Patient Questionnaire

**Xarelto Risk Minimization Study
Survey Instructions**

Thank you for agreeing to participate in this study!

Taking part in this study will take approximately 20 to 25 minutes of your time. Your responses will be kept completely confidential and will not be shared with your health care professionals (e.g., surgery or hospital based doctor or nurse).

This survey consists of two questionnaires. Please follow the instructions below to complete the survey. If you have any questions, please ask the study coordinator for help.

Step 1 - Open envelope #1 and complete the first questionnaire. Please do not refer to the Xarelto patient alert card or other Xarelto educational materials while answering the questionnaire.

Step 2 – When you have completed the first questionnaire, place it back into the envelope and seal the envelope.

Step 3 – Open envelope #2. Inside the envelope you will find a Xarelto patient alert card. Please read the Xarelto patient alert card. After you have read it, complete the second questionnaire.

Step 4 - When you have completed the second questionnaire, place it back into the envelope and seal the envelope.

Step 5 – Return both envelopes to the study coordinator.

**Xarelto Risk Minimization Study
Patient Questionnaire #1**

This is the first of two questionnaires. Please complete this questionnaire before moving on to the second questionnaire (found in a separate envelope).

Please answer the following questions first to confirm that you are eligible for this study.

S1. Are you 18 years of age or older?

- Yes
- No (If no, please speak with the study coordinator to confirm your eligibility.)

S2. Have you taken Xarelto (also known as rivaroxaban) in the past 3 months?

- Yes, I have taken Xarelto in the past 3 months
- No, I have not taken Xarelto in the past 3 months
- I don't know

The purpose of this study is to learn more about your knowledge and understanding of the safety information related to Xarelto (rivaroxaban).

Please do not look at the Xarelto patient alert card while answering the following questions.

Q1. Are you currently taking Xarelto?

- Yes
- No
- I don't know

Q2. Approximately how long have you been taking Xarelto?

Select the one answer that best applies to you.

- Less than 1 month
- Between 1 and 6 months
- More than 6 months but less than 1 year
- More than 1 year
- I don't know

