- I don't know

Q5. I need to speak to my doctor prior to any intake of other medication(s).

- Yes, this is true
- No, this is not true
- I don't know

Q6. I need to inform my doctor or dentist about Xarelto intake prior to any kind of surgery or invasive procedure.

- Yes, this is true
- No, this is not true
- I don't know

Q7. I need to tell my doctor right away if I have any signs or symptoms of bleeding while taking Xarelto.

- Yes, this is true
- No, this is not true
- I don't know

Q8. Should Xarelto (15 mg and 20 mg tablets) be taken with food?

- Yes
- No
- I don't know

Q9. What should you do to ensure Xarelto is effective in preventing blood clots?

Select all that apply.

- Take Xarelto exactly as prescribed by your Health Care Professional
- Take Xarelto only when you do not feel well
- Do not miss a dose of Xarelto
- I don't know

The next section is about the Xarelto Patient Alert Card that you reviewed before completing the second questionnaire. The Xarelto Patient Alert Card contains important safety information about Xarelto.

Q10. Prior to today, had you received or been given the Patient Alert Card for Xarelto?

- Yes → **Go to Q11**
- No → **Go to Q15**
- I don't remember → **Go to Q15**

Answer questions Q11 – Q14 only if you received a Patient Alert Card for Xarelto.

Q11. Prior to today, had you ever read the Patient Alert Card for Xarelto?

- Yes → **Go to Q13**
- No → **Go to Q12**
- I don't remember → **Go to Q13**

Q12. Is there a reason why you have not read the Patient Alert Card for Xarelto, prior to today?

Select all that apply.

- I haven't taken the medication yet
- Someone else explained it to me
- I lost the patient alert card
- I already knew the information
- I have not had the time yet
- I am not interested in reading it
- Other

Q13. How much of the time do you keep the Xarelto Patient Alert Card with you?

Select the one answer that best applies to you

- All the time
- Some of the time
- None of the time
- I don't know

Q14. Who do you show the Patient Alert Card to?

Select the one answer that best applies to you

- Every doctor or dentist that I visit
- No one, it is just for my information
- Only to healthcare professionals who ask for it
- I don't know

Q15. Prior to today, had someone explained the information in the Patient Alert Card for Xarelto to you?

Select all that apply.

- Yes, a doctor
- Yes, a nurse
- Yes, a pharmacist or someone at the chemists
- Yes, a friend, family member, or carer
- No

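### Patients who have stopped rivaroxaban are eligible, but the items on keeping and showing the alert card are in the present tense and have no answer for them, so on-treatment carrying is not clearly measured in this group

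*Protocol*

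**What the plan says.** Eligibility rests on recent use, not current use. Section 3.2.2 reads "Patient has taken rivaroxaban within the last 3 months for prevention of stroke and systemic embolism", continuing with the venous thrombosis indication, and Section 3.2.3 repeats it: "Patients will be eligible if they have taken rivaroxaban within the last 3 months for either SPAF or DVT treatment and secondary prevention". Screening item S2 in Appendix D uses the same 3-month window.

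Questionnaire #1 allows for patients who have stopped. Its first item is "Are you currently taking Xarelto", with yes, no and don't-know answers. A 'no' ends nothing and skips nothing.

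Questionnaire #2 Q13 asks "How much of the time do you keep the Xarelto Patient Alert Card with you", with answers all, some or none of the time, or don't know. Q14 asks, also in the present tense, to whom the card is shown. The only filter before these items is Q10, receipt of a card before that day.

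Section 5 says the study will evaluate "whether the patient carries the patient alert card during treatment". The third objective in Section 2 is to determine whether patients use and carry the card; it has no wording about the treatment period. Section 3.2.5 calls the questionnaire in Appendix D final, apart from country-specific changes. Section 4 leaves subgroups, missing data and tables to a separate analysis plan.

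**The concern.** A patient who finished treatment some weeks ago and put the card in a drawer is eligible and, if a card was received, must answer Q13 and Q14. The card states that its holder is under anticoagulant treatment, so such a patient has a good reason not to carry it. No response says so. Read literally, the closest answer to Q13 is 'none of the time', which is the same answer as that of a patient on treatment who leaves the card at home. By contrast, Q12 does offer an answer for a patient who has not yet taken the drug, although that patient is not eligible.

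Carrying and using the card is a named objective. If the two kinds of answer are mixed, the reported rate partly reflects how many respondents have stopped. That share may differ by indication: the prescriber guide in Appendix A describes treatment in atrial fibrillation as long term, but says of DVT and PE "The duration of therapy should be individualised after assessment of the treatment benefit against the risk for bleeding". Three assessments are planned, at 18 months, 3 years and 7 years, and a changing share of former users could look like a change in behaviour.

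**Working it through.** **1. The protocol's own precision.** Section 3.2.4 and Table 2 use p ± 1.96 × √(p(1−p) × DE / n), where the design effect DE is 1, 2 or 4 for an intraclass correlation (ICC) of 0, 0.11 or 0.33 with 10 patients per practice. For n = 500 and p = 50%:

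| ICC | DE | Half-width (points) | Interval | Table 2 |
|---|---|---|---|---|
| 0 | 1 | 4.4 | 45.6 to 54.4 | 45.6 to 54.4 |
| 0.11 | 2 | 6.2 | 43.8 to 56.2 | 43.8 to 56.2 |
| 0.33 | 4 | 8.8 | 41.2 to 58.8 | 41.2 to 58.8 |

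The table reproduces.

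**2. Effect of pooling.** Let f be the share of former users among card recipients, a the carrying rate in current users and b the rate reported by former users. The pooled rate is (1−f)a + fb, so the bias relative to a is −f(a−b). The documents give none of f, a or b; every value below is an assumption.

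With a = 70% and b = 10%:
- f = 10%: 0.90 × 0.70 + 0.10 × 0.10 = 64%, bias −6 points.
- f = 25%: 0.75 × 0.70 + 0.25 × 0.10 = 55%, bias −15 points.

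With a = 80%, over a wider range of b:

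| f | b = 0 | b = 40% | b = 80% |
|---|---|---|---|
| 5% | −4 | −2 | 0 |
| 10% | −8 | −4 | 0 |
| 20% | −16 | −8 | 0 |
| 30% | −24 | −12 | 0 |

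**3. Comparison with sampling error.** In the 70%/10% example, 6 points exceeds the half-width without clustering (4.4) but lies within those for ICC 0.11 (6.2) and 0.33 (8.8); 15 points exceeds all three. The half-widths assume that all 500 patients answer. Q13 and Q14 go only to card recipients, so the actual intervals will be wider. A bias of this kind does not shrink as n grows.

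**4. Cost of restricting to current users.** With p = 80%, 500 card recipients assumed and the cluster size reduced in proportion to 10(1−f):

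| f | Half-width, ICC 0 | Half-width, ICC 0.33 |
|---|---|---|
| 0 (all patients) | 3.5 | 7.0 |
| 10% | 3.7 | 7.1 |
| 30% | 4.2 | 7.2 |

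The loss of precision is small.

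**5. What an analysis can and cannot repair.** Q1 of Questionnaire #1 separates current from former users, provided the two forms can be linked. It cannot turn a present-tense answer from a former user into a measure of carrying while on treatment, because the items never ask that.

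**The case against.** A reader might infer that former users are counted as non-carriers and that the carrying result is therefore biased. The protocol does not say this. It sets no scoring rule for Q13, no denominator and no pooling of former with current users. Those choices belong to the analysis plan, which is not at hand. The variable needed to separate the groups is already collected, and Section 4 allows stratification by other logical variables. Neither Section 4 nor Section 5 names current use as a stratum, but neither excludes it.

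Nor is it certain how a former user answers. Some will still have the card in a wallet, some will answer for the time they were treated, and some will tick don't know. The 3-month window limits how many have stopped, though by how much is unknown.

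The phrase about carrying during treatment stands in a descriptive sentence of Section 5. The objective in Section 2 has no such limit, so the mismatch is with Section 5 and not with the objective as worded. The harm to comparisons is also partly conjecture: the protocol specifies no test by indication or between assessments, and Section 5 already warns about country-specific conclusions for patients.

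All of this stands. It does not answer the narrower point: whatever the analysis plan says, the items as written yield no clear on-treatment answer from an eligible group.

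**Conclusion.** The concern holds as a weakness of the questionnaire, not as a demonstrated bias in a fixed estimate. Former users are eligible, Q13 and Q14 do not fit them, and Section 5 describes a measure that these items do not clearly give for that group. A downward bias follows only if their answers are pooled with those of current users and if they report carrying the card less often.

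Its size is unknown and starts at zero. The figure of 6 to 15 points rests on assumed values: 70% carrying in current users, 10% in former users, and former users making up 10% to 25% of card recipients. Against the protocol's half-widths of 4.4 to 8.8 points, that runs from less than the clustered sampling error to clearly more than it. Severity is minor to moderate. The change is worth making because it is cheap and because no later analysis can recover the missing information for former users.

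**What to change.** In Appendix D, word Q13 and Q14 of Questionnaire #2 for the treatment period (while you are, or were, taking Xarelto), or add a response saying that the patient no longer takes it. The rewording is preferable because it also obtains on-treatment carrying from former users; the extra response only identifies them.

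Report carrying and showing the card among patients who answer 'yes' to Q1 of Questionnaire #1, and show former users separately.

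Confirm that both questionnaires carry the patient's study number. Section 3.5.3 speaks only of the questionnaire, in the singular, while Appendix D has two forms returned in separately sealed envelopes. Linkage is a reasonable inference but is not stated.

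The cost is a small change of wording and its translations, to be included in the questionnaires that go to ethics review, and a slightly smaller denominator for the main carrying rate.
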